#### 3.5 Study activities

### 3.5.1 Theoretical framework of acceptability (TFA)-based acceptability questionnaire

The theoretical framework of acceptability (TFA) was developed in response to recommendations that acceptability should be assessed in the design, evaluation and implementation phases of healthcare interventions. The TFA consists of seven component constructs (affective attitude, burden, ethicality, intervention coherence, opportunity costs, perceived effectiveness, and self-efficacy) that can help to identify characteristics of interventions that may be improved. Using this robust framework, a validated generic TFA-based questionnaire was developed as an adaptable tool to measure acceptability across various healthcare interventions.

#### 3.5.2 Pre-validating the questionnaire for acceptability of routine retinal screening in persons with SCD

We have adapted the generic TFA questionnaire with insights from our PPI group pilot, expert clinical opinion and literature review. The first draft of the adapted TFA questionnaire has been discussed with our PPI consisting of 10 patients with lived experience of SCD, who also helped us to develop the study design. This

feedback was incorporated and shared with the PPI group and a further group of 10 patients attending retinal screening clinics for SCD at 2 eye units in the UK to check comprehensibility and comprehensiveness. The final version of the questionnaire incorporates this input from patients and medical experts managing patients with SCD.

#### 3.5.3 Other study activities

# Best corrected visual acuity (BCVA) with habitual correction and pinhole

This is a measure of the primary outcome. BCVA will be assessed using the Early Treatment of Diabetic Retinopathy Study vision chart chart in a 4 meter lane under routine clinic conditions as part of routine clinical care as usually conducted. Participants will be invited to bring their most up to date correction to the study visit. BCVA will be recorded with their habitual correction and pinhole in LogMAR. **Refraction by an optometrist is not required** 

# Slit lamp biomicroscopy and dilated funduscopy

Slit lamp biomicroscopy allows the ophthalmologist to microscopically examine the eye for any abnormalities or problems. Dilated funduscopy allows better evaluation of the lens and vitreous. This will be performed to document other ocular causes of visual impairment such as corneal scars, cataracts and vitreous haemorrhage.

#### Spectral domain OCT

Spectral domain OCT (SD-OCT) is the current reference standard for diagnosing and monitoring progression of various macular diseases. It is non-invasive and rapid, often taking less than 15 seconds to capture a detailed assessment of the macular. It captures the cross-sectional morphology of retinal structures and allows detailed assessment of anatomical layers affected by the disease. In sickle cell maculopathy, there is evidence of retinal thinning, with the temporal retina being most commonly affected. All images will be assessed by the ophthalmology team and management instituted as per standard of care. The interpretation of the images will be documented in the study case report form

#### OCT angiography

OCT-Angiography (OCT-A) is now often routinely performed as part of routine clinical care and provides depth-resolved visualisation of the superficial and deep capillary plexuses. By allowing depth-resolved visualization of the macular vascular network with high resolution, optical coherence tomography angiography (OCTA) recently detected much more macular vascular alterations than previously detected using just OCT and provided additional features, including enlargement and irregularities of the foveal avascular zone (FAZ), hairpin venular loops, and areas of flow loss responsible for irreversible macular thinning. All images will be assessed by the

ophthalmology team and management instituted as per standard of care. The interpretation of the images will be documented in the study case report form

### Ultra-widefield fundus photography

Ultra-widefield fundus photography captures an image covering more than 80% of the retina. It allows the observer to assess the retina, associated blood vessels and optic nerve. This is particularly of benefit in sickle cell retinopathy, where the initial stages of proliferative retinopathy occur in the far periphery and can be missed if the periphery is not carefully assessed. In the UK, Optos imaging and the Zeiss Clarus are the most commonly used ultra-widefield imaging systems. All units included in this study will be using either the Optos or the Clarus. Whilst there is evidence that un-dilated ultrawide field fundus photography can be of utility in screening for sickle cell retinopathy with a specificity of 100% compared to dilated funduscopy examination in one study, the sensitivity was 69.2%. Therefore, for the purpose of this study, ultra-widefield fundus photography will be performed with a dilated pupil. All images will be assessed by the ophthalmology team and management instituted as per standard of care. The interpretation of the images will be documented in the study case report form

#### **NEI-VFQ 25**

The NEI-VFQ 25 is a validated 25 item questionnaire comprising of 11 subscales on different aspects of vision-related functioning (VRQoL), quality of life and 1 item on general health. It is the most commonly used patient reported outcome measure in retinal research and trials. It is designed to assess the influence of visual impairment on vision-related function and multiple dimensions of VRQoL. This instrument has evidence of good psychometric properties, including reliability and construct validity, assessed using classical test theory in a mixed population of patients with various eye diseases and visual impairment.

Due to the proliferation of diagnostic hubs in the NHS, the NEI-VFQ-25, which can take up to 15 minutes to complete may limit recruitment at some sites. As such, we will monitor the impact of completing this questionnaire on recruitment through our monthly investigators meeting for the first 3months of recruitment. Feedback from Principal Investigators on the impact of the NEI-VFQ 25 on recruitment will determine whether to switch to the EQ-5D with vision bolt-on.

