# **Study summary**

Study Title	The Sickle Eye Project: Prevalence of visual impairment due to sickle cell retinopathy and maculopathy in the United Kingdom	
Short title	The Sickle Eye Project	
Study Design	Cross-sectional, non-interventional study	
Study Participants	People with Sickle cell disease	
Planned Size of Sample (if applicable)	600 patients with sickle cell disease	
Planned recruitment Period	12 months	
Research objectives	
 
Primary objective: To determine the prevalence of visual impairment (best corrected visual acuity ≥ LogMAR 0.3 in at least one eye) due to sickle cell retinopathy (SCR) and/or maculopathy in persons with sickle cell disease (SCD)
 
Secondary objectives:         
 
To determine the prevalence of each stage of SCR and maculopathy and correlation with:                   

	

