### 2.Study Objectives

The Sickle Eye Project includes an internal pilot phase, which is the first 4 months of the recruitment period, to assess recruitment and trial processes.

The objectives of the internal pilot are:

- 1. To open 6 sites by the end of the pilot phase
- 2. 95% of the expected monthly recruitment is achieved by the end of the pilot phase
- 3. Adherence to imaging protocol in ≥90% of cases
- 4. 95% of recruited participants with completed NEI VFQ 25 questionnaire

Main study primary objective: To determine the prevalence of visual impairment (best corrected visual acuity ≥LogMAR 0.3 in at least one eye) due to SCR and/or maculopathy in persons with SCD

Main study secondary objectives:

- 1. To determine the prevalence of each stage of SCR and maculopathy and correlation with:
- i) number of hospital admissions with acute sickle cell episode in the past 12 months, ii) serum HbF level iii) serum Hb level
- 2. To determine the impact of SCR and maculopathy on vision-related quality of life.
- 3.To determine the acceptability to patients of retinal imaging and routine screening for SCR and maculopathy.

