# Recruitment progress

Green: Recruitment of >120 at end of pilot phase

Amber: Recruitment of < 120 but ≥ 79 patients at end of pilot phase

Red: Recruitment of <79 patients at end of pilot phase.

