#### Completion of the NEI VFQ-25

100% of recruited participants completing the NEI VFQ-25

Green: ≥95% of recruited participants with completed NEI VFQ-25

Amber: ≥80% of recruited participants with completed NEI VFQ-25

Red: <80% of recruited participants with completed NEI VFQ-25

If at the end of the pilot phase the thresholds are at amber or red for any of the progression decision points, the Co-Investigator Group, which includes a lived experience expert as co-applicant will review and provide remedial action that would allow progression to the main trial to the Funder. If there are no obvious remedial actions that can be taken, the Co-Investigator group will discuss stopping the trial with the Funder.

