### 3. Overall study design

## 3.1 Study design

This is a cross-sectional, non-interventional study. Potential participants will be introduced to the study by their haematologist, who will also provide them with the participant information sheet. Identification of potential participants in the haematology clinic is important to prevent ascertainment bias and sample a representative

sample of people with SCD. All patients with SCD are offered regular specialist follow-up by a haematologist in the UK. The national haemoglobinopathy registry record for 2021 reported 12904 people with SCD confirming that an overwhelming proportion of SCD patients are under specialist care in the UK. Informed consent will be obtained from willing participants by the ophthalmology team either in the eye department or over the telephone. Informed consent will be obtained prior to the collection of any data. Once consented, participants will have best corrected visual acuity (BCVA) with habitual correction and pinhole measured, a slit lamp examination of the anterior segment and fundus, spectral-domain optical coherence tomography (SD-OCT), optical coherence tomography-angiography (OCT-A) and ultra-widefield fundus photography performed in the eye department. Subsequently, the participant will have the NEI VFQ-25 questionnaire and the acceptability of retinal screening questionnaire administered.

In some departments, it may be more appropriate for the haematology team to share brief details about the study, including the study leaflet with potential participants. Interested participants can be sent the participant information sheet ahead of their eye clinic appointment.

The NEI VFQ-25 questionnaire can be administered over the telephone either at the time of consent or after the visit to the eye department. The acceptability of retinal screening questionnaire has to be administered after the retinal imaging has been performed.

If the NEI VFQ-25 is completed over the telephone, this must be done ±28 days of the eye clinic visit for examination and retinal images.

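### The pilot rules do not fit together: a questionnaire switch allowed inside the pilot would by itself defeat the NEI VFQ-25 completion criterion, and the green recruitment band cannot be traced to the 95% objective

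*Protocol*

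**What the plan says.** **Questionnaire.** Protocol section 3.5.3 notes that the NEI VFQ-25 can take up to 15 minutes and might limit recruitment at some sites. Its impact is reviewed at monthly investigator meetings for three months, and then: "Feedback from Principal Investigators on the impact of the NEI-VFQ 25 on recruitment will determine whether to switch to the EQ-5D with vision bolt-on". No numerical trigger, switch date or scope (one site or all) is given.

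The internal pilot is defined in section 2 as a phase "which is the first 4 months of the recruitment period". One of its progression criteria in section 2.1 is "Green: ≥95% of recruited participants with completed NEI VFQ-25", with red below 80%. An amber or red result sends the study to the co-investigator group for remedial action, and to a discussion of stopping with the funder if no remedy is obvious. Section 5.1 correlates only the NEI VFQ-25 global score with acuity, SCR stage and maculopathy. The EQ-5D with vision bolt-on is described in section 3.5.3, but it has no place in the outcomes, the pilot criteria, the activity table or the analysis. Section 3.1 already offers a route that saves clinic time: "The NEI VFQ-25 questionnaire can be administered over the telephone", within 28 days either side of the eye visit.

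**Recruitment.** Pilot objective 2 in section 2 is "95% of the expected monthly recruitment is achieved by the end of the pilot phase". The expected monthly figure is not stated. Section 2.1 scores a cumulative count instead: "Green: Recruitment of >120 at end of pilot phase" and "Amber: Recruitment of < 120 but ≥ 79 patients at end of pilot phase". The Study summary plans "600 patients with sickle cell disease" over 12 months.

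**The concern.** The pilot decides whether the study continues, so its rules should not defeat one another. Here one rule permits the instrument to be replaced while another, a month later, counts only completions of the instrument being replaced. A switch made to protect recruitment could therefore produce a red score that says nothing about how well sites collect quality-of-life data.

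A switch would also leave no instrument common to all participants for main-study secondary objective 2 (vision-related quality of life), while the only written analysis uses the score of the discontinued instrument. Later analysis cannot recover a questionnaire that was never given.

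On recruitment, a threshold that cannot be derived from its own objective cannot show whether that objective was met. A count that belongs to no band leaves the decision open at exactly the boundary.

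**Working it through.** **Inputs (Protocol).** 600 participants in 12 months (Study summary); pilot of 4 months (section 2); monitoring window of 3 months (section 3.5.3); completion bands of 95% and 80%, recruitment bands of 120 and 79 (section 2.1); 6 sites open by the end of the pilot (section 2) of up to 16 (section 3.3); 554 evaluable of 600 (section 5).

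**(a) Highest attainable NEI VFQ-25 completion at month 4.** Assume that all sites switch at the end of month 3 and that completion before then is perfect. The ceiling is recruits in months 1–3 divided by recruits in months 1–4. The protocol gives no accrual curve, so three assumed shapes are shown:

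- Flat: 150/200 = 75%.
- Step ramp of 12.5, 25, 37.5 and 50 per month: 75/125 = 60%.
- Continuous linear ramp: (3/4)² = 56%.

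All are below 80%, so all score red.

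Scope matters. Under flat accrual, month 4 supplies 25% of pilot recruits. If a fraction f of them is switched, the ceiling is 1 − 0.25f. Green needs f ≤ 0.05/0.25 = 20%, and avoiding red needs f ≤ 0.20/0.25 = 80%. Under the step ramp month 4 supplies 50/125 = 40%, and the limits become 12.5% and 50%.

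**How the sample would divide.** Flat accrual gives 3 × 50 = 150 of 600 with the NEI VFQ-25 (150 × 554/600 ≈ 139 evaluable) and 450 with only the EQ-5D (≈ 416 evaluable). If the pilot recruits 120 in total, the NEI VFQ-25 group is 120 × 0.75 = 90, 120 × 0.60 = 72 or 120 × 0.5625 ≈ 68.

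Correlation detectable with 80% power at two-sided 5%, by the Fisher z approximation, tanh[(1.96 + 0.8416)/√(n − 3)]:

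- n = 554: 0.12
- n = 416 (EQ-5D group, flat accrual): 0.14
- n = 139 (NEI VFQ-25 group, flat accrual): 0.24
- n = 83 to 62 (NEI VFQ-25 evaluable if the pilot recruits 120): 0.30 to 0.35

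**(b) Can a count above 120 be reproduced from the 95% objective?**

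- Flat accrual: 600/12 × 4 = 200 expected; 95% is 190; 120/200 = 60%. Not reproduced.
- 120 is itself the expectation: 95% is 114, which scores amber. Not reproduced.
- Working backwards: 120/0.95 = 126.3 expected by month 4.
- Step ramp as above: 125 expected; 95% is 118.75. Close.
- Six sites opening evenly over the pilot, then six to month 12, at equal rates per site: 12 + 48 = 60 site-months, 10 per site-month, so 120 expected and 95% is 114.
- The same pilot, but reaching 16 sites at some point between month 4 and month 12: total site-months from 12 + 128 = 140 down to 12 + 88 = 100, so 600 × 12/140 ≈ 51 up to 600 × 12/100 = 72 expected. Here a count above 120 would be stricter than the objective.

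The objective and the criterion also measure different things. A linear rise to 50 per month at month 4 reaches the flat-average rate by the end of the pilot, but the cumulative count is 0.5 × 50 × 4 = 100, which is amber.

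Exactly 120 is neither above 120 (green) nor below 120 (amber).

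**The case against.** **The switch may never happen, and need not be study-wide.** This stands. Section 3.5.3 fixes a monitoring window, not a switch at month 3, and the stated worry is burden at some sites. A late or local switch could leave the criterion at amber or even green. A red score leads to review, not to automatic stopping.

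**A reader might infer that secondary objective 2 would then rest on a small early subset.** The documents do not support that. Neither the objective nor the matching outcome names an instrument, and under flat accrual about 450 participants would have the EQ-5D with vision bolt-on, which the Protocol describes as valid in people with vision problems. What does shrink is the sample for the one analysis written in section 5.1. An SAP, not shown here, may add an EQ-5D analysis, but it cannot supply a common instrument or change a pilot criterion set in the Protocol.

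**Staged site opening can explain 120.** This also stands. A reader might infer that green should be 190, but that assumes 50 a month from the first day, which a pilot that opens sites in stages does not imply.

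**A reader might also infer that a green pilot is on course to miss the 5% interval width.** That requires the pilot average of 120/4 = 30 a month to continue unchanged to month 12. More sites may open, and (600 − 120)/8 = 60 a month afterwards would reach 600. The Protocol states neither pace, and an amber result calls for remedial action, so no loss of precision is shown.

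**Conclusion.** The point holds in two limited parts.

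(a) As written, the switch provision is inconsistent with the completion criterion and with section 5.1. Given a prompt study-wide switch, the criterion would be unattainable: a ceiling of 75% under flat accrual and 56–60% under the ramps tried, against a red line of 80%. The sample would divide into about 150 with the NEI VFQ-25 (fewer under a ramp) and the remainder with the EQ-5D only. This is conditional on a switch whose trigger, date and scope the Protocol leaves open.

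(b) The green recruitment band agrees with pilot objective 2 only under an unstated expectation of about 126 by month 4. Under other plausible accrual shapes it is laxer or stricter than 95%. The gap at exactly 120 needs no assumption.

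Neither part touches the primary outcome or its sample size. Both concern rules that feed a decision on whether the study proceeds, so they merit correction.

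**What to change.** **Questionnaire.** Choose one:

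- Give the six-question EQ-5D with vision bolt-on to everyone from the first participant, alongside the NEI VFQ-25, so that one instrument covers the whole sample if the longer one is dropped. Cost: a few more minutes per participant, which adds slightly to the burden that section 3.5.3 is trying to limit.
- Keep the NEI VFQ-25 throughout, using the telephone route within ±28 days where clinic time is short. Cost: the option of a shorter form is given up.

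If a switch is retained, state its trigger, date and scope. In either case, word the completion criterion and section 5.1 so that they refer to the instrument assigned to each participant.

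**Recruitment.** State the expected cumulative recruitment at month 4, derived from the site-opening plan. Set green at 95% or more of that figure and start amber directly below it, so that no count (120 at present) is left without a band. The figure should come from the plan; 190 is not a default.

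The overall cost is a protocol amendment and notice to the funder. The green band may move in either direction once the accrual plan is written down.

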# EQ-5D with vision bolt-on

The 5 level EQ-5D is a widely used preference-based health related quality of life instrument with one question for each of 5 core dimensions of health: mobility, self-care, usual activities, pain/discomfort and anxiety/depression. To capture the effect of conditions that affect sensory functions or cognition that may not

be adequately captured by the instrument, additional dimensions, known as 'bolt-ons' were developed. The vision bolt-on has demonstrated enhanced sensitivity, construct validity and responsiveness to change in populations with vision problems. Importantly, EQ-5D with vision bolt-on comprises of 6 questions which can be rapidly completed by participants

Study activity	Personnel	Baseline	±28 days
Eligibility	Haematology team		
criteria check		X	
		*	
Patient	Haematology team	х	
information	Or Ophthalmology team		
sheet	er opmilainiology toain		
Informed	Ophthalmology team	x (Can be completed by	
consent		telephone)	
BCVA with	Ophthalmology team	х	
habitual			
correction and			
pinhole			
Slit lamp	Ophthalmology team	X	
biomicroscopy			
and dilated			
funduscopy			
ОСТ	Ophthalmology team	х	
OCT-A	Ophthalmology team	Х	
Ultrawide field	Ophthalmology team	х	
fundus			
photography			
*NEI-VFQ 25	Ophthalmology team	x (Can be completed by telephone)	Х

*Acceptability	Ophthalmology team	x (Can be completed by	Х
Questionnaire		telephone after retinal	
		imaging and within 14 days)	
Clinical	Ophthalmology	X	
assessment of			
images			
Completion of	Ophthalmology/haematology	Х	Х
case report	team		
form			
Transfer of	Ophthalmology team	X	Х
images			

#### 4.Image acquisition protocol and transfer of data

Imaging acquisition will be performed by trained staff at each recruitment site. As this is a pragmatic study, and the imaging to be acquired are standard of care in NHS eye departments, standards for training and experience of staff performing the imaging acquisition function will be the ones applicable at each recruitment site as per local Standard Operating Procedures.

The Moorfields Reading Centre will provide supporting material of educational and advisory character for acquisition of high-quality imaging from the Sickle Eye Project participants. It will also provide detailed, yet simple and intuitive instructions for imaging file export and direct upload to the Moorfields Grading Portal Webbased Application.

For details on the process of User activation, including Users with the Uploader role, and User Management, please see relevant provisions of the 'Data Protection and Information Security' section.

For each patient, imaging from the three following modalities will be obtained, and transferred to the Moorfields Reading Centre. Imaging from both eyes will be obtained:

- Optical Coherence Tomography scan (TopCon 3D-2000, Heidelberg Spectralis or Zeiss Cirrus).

Recommended parameters: Macula Centre 6x6 mm Raster Scans.

- Optical Coherence Tomography Angiography where available (TopCon Triton, Heidelberg Spectralis OCT-2, Zeiss Angioplex)

Recommended parameters: Macula Centre 6x6 OCT Angiography mode

- Wide Field Imaging (Optos California or Zeiss Clarus)

Recommended parameters for wide field imaging: Instructions will be provided to assist Imaging acquisition staff with obtaining clear view of the Fundus, including the extreme periphery through imaging acquisition at the central and 4 peripheral positions of gaze (up, down, right, left) and the avoidance of 'eyelash' artifacts that interfere with Fundus view in Optos Ultra-Wide Field Imaging.

The images being transferred to Moorfield hospital will be link anonymised with no patient identifiers. The link key will remain with each recruiting site and will not be shared with the sponsor site.

Bi-directional communication between recruitment sites and the Moorfields Reading Centre will be possible through the interactive Moorfields Grading Portal. A granular Audit Log will record all study-related activity, including who, where and when each activity was performed.

